COMBINED CBT and tDCS INTERVENTION EFFECTS ON PAIN PERCEPTION: To directly address the aims of the present proposal, in a recent preliminary pilot, the Investigators examined the effects of anodal versus cathodal tDCS over the left DLPFC in combination with a laboratory CBT intervention on thermal pain tolerance in 8 healthy volunteers. Participants underwent repeated heat tolerance testing using the Medoc Pathway system before, during and after the combined tDCS+CBT intervention. Participants were randomly assigned to receive anodal or cathodal tDCS delivered over the left DLPFC. For this preliminary pilot, participants all listened to a recording of a laboratory-version of a CBT intervention that focused on 3 distinct elements: 1) identification of catastrophizing language and replacement with more realistic and attenuated linguistic tags for thermal experiences. 2) identification and challenging of automatic negative self-effacing thoughts related to the tolerance task, and 3) a behavioral distraction strategy. Anodal tDCS applied to the left DLPFC during the CBT intervention was associated with a significant increase in thermal pain tolerance whereas cathodal stimulation appears to have blunted the analgesic benefit of the CBT intervention. Despite all subjects receiving the same CBT intervention, those that received simultaneous anodal stimulation of the left DLPFC found the CBT intervention significantly more helpful ($p<.05$) and found the strategies presented more useful in improving pain tolerance ($p<.05$) than those who received cathodal stimulation. These findings support the notion that engaging cognitive neural circuits that have been shown to play a role in the

down-regulation of pain experience and then exciting the circuits with tDCS might offer synergistic benefit.

D. RESEARCH DESIGN AND METHODS (including data analysis)

OVERVIEW: Pilot clinical trial-- Patients with FM will receive a brief course (6 sessions) of manualized CBT for pain (or education-only control) combined with anodal or sham tDCS over the left DLPFC

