PARTICIPANTS: Participants will be 72 patients meeting the American College of Rheumatology (ACR) criteria from diagnosis of fibromyalgia for at least 1-year. Patients must not have any chronic pain conditions other than fibromyalgia, and must not be on chronic opioid therapy for pain. Patients with a history of seizures, who are or might be pregnant, or with metal/electronic implants or devices above the waist will be excluded to ensure tDCS safety. Patients with moderate to severe depression (HRDS>18) at the time of randomization will be excluded, however patients with no depression or only mild depression (HRDS<19) will be eligible provided that the onset of the first depressive episode was after the onset of fibromyalgia (as is commonly seen in patients with chronic pain) in order to exclude patients for whom chronic widespread pain might be a somatic manifestation of the depressive illness. To be eligible for enrollment, BAI scores must be <16 to limit the sample to patients with minimal to no clinical anxiety problems.

tDCS METHODS: tDCS will be delivered in 30-minute-sessions and will be conducted with the Phoresor-II Auto (Model PM850) using 2mA current. This constant current device ramps up to the desired amplitude to minimize discomfort for participants and ramps the amplitude back to 0mA at the end of the session. Electrodes will be standard small (4cm X 4cm) sponge electrodes soaked in a sterile solution of 0.9% sodium chloride insulated by a latex casing. The current density and total charge delivered by the above parameters is consistent with those used safely in the current research literature on tDCS. In all tDCS conditions, participants will undergo anodal stimulation of the left DLPFC (Brodmann Area 9; BA9) and cathodal stimulation of the right DLPFC (which is consistent with the majority of published prefrontal tDCS studies for pain to date) during each of the 6 CBT sessions. The electrodes will be fastened with Velcro strap(s). Specially designed software (by the Investigator) interfaces with an ONTRAK ADU218 Solid State Relay I/O interface connected to the tDCS device permitting normal and reverse current flow between the electrodes in a manner that is completely masked. The software reads the assigned condition directly from an encrypted subject-randomization-file and delivers anodal, cathodal or sham stimulation in a blinded fashion.

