THE BECK DEPRESSION INVENTORY (BDI) is a well-researched, brief self-report depression-screening instrument. This instrument will be used for screening purposes in the laboratory study and to characterize depression in the clinical cohort. The BDI scale assesses suicidal ideation, those patients exhibiting suicidal ideations will be referenced to a therapist in order to further manage their depressive symptoms.

THE BECK ANXIETY INVENTORY (BAI) is a well-researched, brief self-report anxiety-screening instrument. It assesses different aspects of anxiety experience (e.g., physiological, cognitive, behavioral).

THE BRIEF PAIN INVENTORY (BPI) is a self-report questionnaire designed to assess pain intensity and the impact of pain on general functioning, relationships and mood.

DAILY PAIN/MOOD DIARIES will be administered via paper and pencil to patients in the clinical pilot Diaries will assess daily (via VAS) average pain, pain at its worst, pain unpleasantness, mood, activity level, and will capture hours of sleep and sleep quality ratings.

THE MCGILL PAIN QUESTIONNAIRE (MPQ) is a self-report scale designed to capture the quality and intensity of pain experience. The ratings load onto 4 factors: 1) Sensory, 2) Affective, 3) Evaluative, and 4) Miscellaneous.

THE MOS SHORT-FORM12 HEALTH SURVERY (SF12) will be used to assess quality of life across the eight QOL domains captured with the measure during the trial.

THE FIBROMYALGIA IMPACT QUESTIONNAIRE will be used to assess pain symptoms and functioning specific to FM.

PROCEDURES:

Clinical Pilot Trial: Patients will be recruited by fliers or referred by providers in the Chronic Pain Clinic, Dept. of Rheumatology and the Behavioral Medicine Clinic at MUSC. Participants will be screened on the telephone, consented, oriented to the study, and instructed in the use of pain diaries. After a 2-week baseline phase, patients will undergo QST. They will then start the manualized CBT intervention in the Behavioral Medicine Clinic at MUSC with simultaneous tDCS (real or sham; randomized and masked). Participants will undergo 1 session per week for 6 weeks. After the last session, participants will undergo another QST session. Patients will continue to complete the pain diaries throughout the treatment as well as a 4-week follow-up phase. At 3 and 6 months, participants will return to the lab to re-complete the dependent measure battery.

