DATA ANALYSIS PLAN AND POWER: Hierarchical Linear Modeling (HLM) will be used to examine changes in pain, sleep and activity over time while controlling for mood (time-series), and controlling for

baseline depression, anxiety and pain scores as a function of group (active vs sham tDCS). HLM will also be used to examine changes in quality of life and functional impairment due to pain. Previous research on the effects of CBT for pain and of tDCS for pain suggests that each is associated with a medium effect-size. To be conservative, assuming that there is no synergistic interaction-effect of combined tDCS and CBT, power is good to detect a group-level main effect ($1-\beta>.80$) with as few as 18 subjects per group. If the interaction-effect is large, as is expected, power is excellent to detect main and interaction effects ($1-\beta>.90$).

E. PROTECTION OF HUMAN SUBJECTS

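### The plan does not say how each outcome's own baseline enters the model; in an ordinary group-by-time model the group contrasts have only change-score precision, which can be improved at no cost

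*Combined protocol and SAP*

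**What the plan says.** The whole analysis plan is one paragraph in Section D, Data Analysis Plan and Power. Its first sentence states that "Hierarchical Linear Modeling (HLM) will be used to examine changes in pain, sleep and activity over time while controlling for mood (time-series"), and goes on to control for "baseline depression, anxiety and pain scores as a function of group (active vs sham tDCS"). A second sentence adds that "HLM will also be used to examine changes in quality of life and functional impairment due to pain". That sentence has no covariate list.

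So pain has its own baseline named as a covariate. Sleep and activity do not, and nothing is named for the outcomes measured by the SF-12 and the FIQ. The plan does not say whether baseline is an outcome time point, a covariate or part of a change score.

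Pre-treatment data exist or are implied. Under Dependent Measures, sleep and activity are daily diary items, and under Procedures the diary starts in a 2-week phase before treatment. For the questionnaires, Procedures says that at 3 and 6 months "participants will return to the lab to re-complete the dependent measure battery". This implies an earlier administration, but no baseline visit for it is written out.

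The Overview crosses two factors: "manualized CBT for pain (or education-only control) combined with anodal or sham tDCS over the left DLPFC". With 72 patients in total, equal allocation gives 72/4 = 18 per cell. Both hypotheses in Section A concern functioning as well as pain.

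**The concern.** An outcome's own baseline is usually its best single predictor. Regressing follow-up on that baseline estimates a randomised group difference at least as precisely as comparing changes does. The plan does this explicitly for pain at most, and gives no instruction for the outcomes that carry the functioning half of the hypotheses.

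The adjustment for baseline pain may also achieve nothing. If the baseline diary days stay in the response while baseline pain is also a covariate, the covariate does not sharpen the comparison of change between groups.

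Hypothesis 1b compares CBT plus tDCS with CBT alone, which is 18 against 18 under equal allocation. At that size chance baseline differences are substantial, and precision that can be had without more patients should be taken.

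**Working it through.** **The plan's own figure.** The plan gives no precision figure that depends on baseline handling. Its only relevant number is power above 0.80 "with as few as 18 subjects per group", on the premise for CBT and tDCS that "each is associated with a medium effect-size". Taking medium as d = 0.5 (assumed), two-sided 5% and one measurement, power is 0.31 for 18 v 18 and 0.55 for 36 v 36; one-sided it is 0.43 and 0.68. Averaging three measurements that correlate 0.3 gives 0.82 for 36 v 36. The figure is therefore not reproduced from the stated inputs, but alpha, sidedness and correlations are missing, so this does not prove an error. It also does not show what baseline handling was assumed. It is a separate matter.

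**Inputs.** Equal allocation, one baseline and one follow-up value, equal variances set to 1, and correlation r. The documents give no r; 0.4 to 0.7 is assumed.

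**Large-sample comparison.** Per-patient variance behind the group contrast:
- group-by-time with free baseline means (equivalent to change scores): 2(1−r)
- own baseline as covariate: 1−r²
- ratio: (1−r²)/[2(1−r)] = (1+r)/2

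| r | 2(1−r) | 1−r² | ratio | variance removed |
|---|---|---|---|---|
| 0.4 | 1.20 | 0.84 | 0.70 | 30% |
| 0.5 | 1.00 | 0.75 | 0.75 | 25% |
| 0.6 | 0.80 | 0.64 | 0.80 | 20% |
| 0.7 | 0.60 | 0.51 | 0.85 | 15% |

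In whole-trial terms, 72/0.85 = 85 and 72/0.70 = 103 patients.

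**At 18 per arm.** Estimating the slope costs a little. In 4,000 simulated trials per value of r:

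| r | change contrast | own-baseline covariate | ratio |
|---|---|---|---|
| 0.4 | 1.195 | 0.891 | 0.75 |
| 0.55 | 0.901 | 0.718 | 0.80 |
| 0.7 | 0.593 | 0.534 | 0.90 |

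This is a gain of about 10–25%, as if each arm of 18 held 18/0.90 = 20 to 18/0.75 = 24 patients. As a check, the theoretical penalty for the slope is 1 + 1/(36−4) = 1.031. It gives ratios of 0.70 × 1.031 = 0.72, 0.775 × 1.031 = 0.80 and 0.85 × 1.031 = 0.88, which agree within simulation error.

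**Power.** At r = 0.6 and d = 0.5 (two-sided 5%, large-sample variances), moving from 0.80 to 0.64 raises power from 0.65 to 0.74 for 36 v 36, and from 0.37 to 0.45 for 18 v 18.

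**Baseline pain as covariate with baseline rows kept in the response.** A covariate that is constant within a patient shifts the baseline and follow-up rows equally, so it cancels from the within-patient difference. In the simulation the group-by-time estimate changed by only about 1e-15, and its variance stayed at the change-score value. The gain returns if the response is follow-up only or a change score, or if the covariate is allowed to interact with time.

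**Diary means.** Suppose any two diary days correlate equally at q. Two 14-day means then correlate at 14q/(1+13q):
- q = 0.3: 4.2/4.9 = 0.86, ratio (1+0.86)/2 = 0.93, gain 7%
- q = 0.5: 7/7.5 = 0.93, ratio (1+0.93)/2 = 0.97, gain 3%

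Serial decay, or patients following different courses, would lower r and raise the gain.

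**Baseline as a response with a common mean.** At r = 0.6 and 36 v 36, simulated variance was 0.628 for this model and 0.637 for the covariate model. The two are equivalent for practical purposes.

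**The case against.** A reader might infer that sleep, activity, the FIQ and the SF-12 are analysed without their baseline values. The documents do not support that: both sentences model change, and change needs a pre-treatment value. Nor do they show that adjustment for the FIQ and SF-12 is limited to depression, anxiety and pain. That list belongs to the first sentence; the second is silent, not restrictive.

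A larger loss is also tempting. Against an analysis of follow-up values alone, the variance factor is 1−r², so intervals would be 8–29% narrower (√0.84 = 0.917; √0.51 = 0.714). The plan does not describe such an analysis, so that comparison does not apply.

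The strongest objection is that the loss depends on a model the plan leaves open. With a common baseline mean there is none. For pain there may be none either, if the response excludes baseline rows. For highly correlated diary means it is small. The other baseline covariates may already capture part of what own baseline would add, which shrinks the gain further. They do so only if they are allowed to act on change, because as main effects they cancel just as baseline pain does. All of this stands and makes the size conditional. It does not remove the point, because the text does not impose the common-mean constraint, and the usual reading of change over time by group leaves baseline means free.

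Finally, Hypothesis 1a can be read as improvement within the CBT arm. The ratios above concern differences between groups, and a rule banning baseline from the response would make that within-arm estimate harder to obtain. This also stands, and the fix allows for it.

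**Conclusion.** The point holds as a conditional loss of precision arising from an unspecified model. It is not an omission of baseline data. If the HLM is the usual group-by-time model with free baseline means, using each outcome's own baseline would cut the variance of the between-group contrasts by 15–30% in large samples, and by about 10–25% in simulation at 18 per arm, for r of 0.4 to 0.7. The cut is about 3–7% for diary means with r near 0.9, less again where other covariates already explain part of the change, and about zero if baseline has a common mean across arms. These figures assume one baseline and one follow-up summary, equal variances and no dropout, and r is not given in the documents. The change is worth making because the comparison for Hypothesis 1b is small and the adjustment needs no more patients.

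**What to change.** Add to the analysis plan, for every outcome, that between-group effects are estimated using that outcome's own baseline: the 14-day diary mean for pain, sleep and activity, and the baseline score for the FIQ, SF-12, BPI and MPQ. Choose one of two forms, not both for the same outcome:
- own baseline as a covariate, with only post-randomisation values as the response; or
- baseline as a response time point, with its mean constrained equal across arms.

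The second form also gives the within-arm change that Hypothesis 1a may need, and it keeps patients whose baseline value is missing. Keep baseline depression and anxiety as further covariates.

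State under Procedures that the questionnaire battery is first given before the first treatment session.

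The cost is a few sentences. The diary baselines are already planned. No extra data are needed for the questionnaires, provided the earlier administration implied under Procedures takes place before treatment.

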1. RISKS TO THE SUBJECTS

The sample will be 72 patients with chronic pain due to FM (BPI pain on average score $>4/10$) between the ages of 21 and 85, with a duration of illness of at least 1 yr and the diagnosis of FM. Interested participants will review and sign the informed consent document with one of the study investigators. Participants will be excluded if they have uncontrolled epilepsy, metal implants in the head or known brain tumors or lesions that intersect the area of stimulation, and severe latex allergies. If a participant indicates the possibility of pregnancy, a urine pregnancy test will be administered. Participants will be excluded from the study if they screen positive for pregnancy. Participants will also be screened for a history of closed head injury with loss of consciousness lasting more than 5 minutes, a history of seizures, a family history of seizures, metal implants above the waist, eczema or other sensitive skin conditions, and current medication usage. These screening measures will be used to assess the risk to benefit ratio for inclusion in the study on a case-by-case basis. If participants indicate on the BDI intent to harm themselves, they will be evaluated by a study psychologist. Pending results of the evaluation, participants will be admitted or hospitalized for appropriate care as necessary. There is no safety data to suggest increased risk for the older population, age 75-85, in this study. There is a possibility of increased skin irritation in this older population.

Targeted/Planned Enrollment Table

Total Planned Enrollment 72

TARGETED/PLANNED ENROLLMENT: Number of Subjects			
Ethnic Category	Sex/Gender		
	Females	Males	Total
Hispanic or Latino	2	1	3
Not Hispanic or Latino	42	27	69
Ethnic Category: Total of All Subjects*	72		
Racial Categories			
American Indian/Alaska Native	1	1	2
Asian	2	1	3
Native Hawaiian or Other Pacific Islander	1	1	2
Black or African American	19	9	28
White	22	15	37
Racial Categories: Total of All Subjects*	45	27	72

b. Sources of Materials

We will collect patient-reported depression, anxiety, sleep, activity, pain scores, and QST scores. All of the data will only contain a unique study identifier. The digital file containing identifying information will be kept on the PI's locked and secure computer. Only the PI and primary research assistant will have access to the identifying information.

c. Potential Risks

tDCS has been found to be safe in humans with mild procedural side-effects such as tingling sensations under the sponge electrodes (experienced by 70% of tDCS patients), moderate fatigue (35%), and light itching sensations under the sponges (30%). After tDCS, the incidence of side-effects is lower but include headache (12%), nausea (3%) and insomnia (<1%) (Poreisz et al, 2007). If tDCS is delivered at 2mA for 20 minutes per day, every day for 4 or more days in a row, mild skin lesions have been reported. However, these lesions have all been reported to heal without scarring within 1 to 3 weeks following the end of tDCS treatment (Palm et al, 2008). All patients will be inpatient at MUSC and under the care of a licensed physician. Qualified nurses and physicians are available 24 hours a day to handle any and all potential complications if they occur.

The current-density of the proposed treatment is 0.125mA/cm² which is substantially less than the current density required to induce brain tissue damage (25mA/cm²). Further, the current (2mA) is over 400 times less than the average current used to induce seizures in electro-convulsive therapy (800mA). While this treatment is indeed investigational and the potential long-term effects are largely unknown, the parameters we plan to use appear to be extremely safe and are within the range used in the published tDCS-pain literature. The risks associated with the use of topical creams (benzocaine and vitamin-E/Aloe) are minimal but include skin irritation and contact dermatitis. If these occur, the investigators will immediately remove any cream from the subject's skin and apply a wet compress.

In a very recent study of tDCS effects on post-operative TKA pain, there were no adverse events associated with tDCS. The most common side effects reported by participants were mild tingling and itching under the electrodes. The benefits of this study appear to outweigh the risks as the slopes of the cumulative PCA usage curves were significantly different between the real and sham tDCS groups; those TKA in the real tDCS group used 44% less PCA dilaudid at 48-hours post-op than did the sham tDCS group. Despite significantly lower PCA dilaudid levels, VAS ratings of pain-on-average were also significantly lower in the real tDCS group ($t(37)=2.28$, $p=.029$).

2. ADEQUACY OF PROTECTION AGAINST RISKS

a. Recruitment and Informed Consent

Participants will be excluded if they have uncontrolled epilepsy, metal implants in the head or known brain tumors or lesions that intersect the area of stimulation, and severe latex allergies. If a participant indicates the possibility of pregnancy, a urine pregnancy test will be administered. Participants will be excluded from the study if they screen positive for pregnancy. Participants will also be screened for a history of closed head injury with loss of consciousness lasting more than 5 minutes, a history of seizures, a family history of seizures, metal implants above the waist, eczema or other sensitive skin conditions, and current medication usage. These screening measures will be used to assess the risk to benefit ratio for inclusion in the study on a case-by-case basis. If participants indicate on the BDI intent to harm themselves, they will be evaluated by a psychiatrist or psychologist from the Institute of Psychiatry. Pending results of the evaluation, participants will be admitted or hospitalized for appropriate care as necessary. There is no safety data to suggest increased risk for the older population, age 75-85, in this study. There is a possibility of increased skin irritation in this older population.

b. Protection against Risk

There is a risk of a loss of confidentiality of your personal information as a result of participation in this study. Qualified nurses and physicians are available 24 hours a day to handle any and all potential complications if they occur.

3. POTENTIAL BENEFITS OF THE PROPOSED RESEARCH TO THE SUBJECTS AND OTHERS

All participants might receive benefit from the CBT intervention. Participants receiving real tDCS+CBT may experience less chronic pain resulting from their fibromyalgia than they would have without the tDCS treatment. Previous investigations suggest that those patients receiving real tDCS and a cognitive behavioral therapy treatment may receive an increased analgesic effect in the treatment of their chronic pain.

